10.4.3 Analysis of the Secondary Endpoint(s)

The same analyses will be used for secondary endpoints.

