4.2 Study Endpoints

4.2.1 Primary Study Endpoints

Primary Endpoint for Registry Study: Proportion of subjects with decreased left ventricular ejection fraction $\geq 10\%$ from baseline at time of hospitalization

Primary Endpoint for Embedded Clinical Trial: Safety of AT-001 based on adverse events reporting

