4.2.2 Secondary Endpoints

Secondary Endpoints (for registry and clinical trial):

- Change in left ventricular ejection fraction
- Change in left ventricular end-diastolic diameter
- Change in left ventricular end-systolic diameter
- Change in biomarkers of cardiac injury
- Frequency of atrial fibrillation
- Frequency of heart block
- Frequency of non-sustained ventricular tachycardia
- Frequency of sustained ventricular tachycardia
- Frequency of ventricular fibrillation

Secondary Endpoints (for clinical trial):

- Proportion of subjects requiring mechanical ventilation
- Proportion of subjects with decrease in left ventricular ejection fraction ≥10% from baseline at time of hospitalization

5 Study Enrollment and Withdrawal

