10.4.2 Analysis of the Primary Efficacy Endpoint(s)

Registry Study

CONFIDENTIAL This material is the property of the NYU School of Medicine and Langone Medical Center. Do not disclose or use except as authorized in writing by the study sponsor Interventional Template Version: 11 January 2019

- Multivariable logistic regression models and Cox Proportional Hazard models will be used to estimate the association between clinical variables at time of hospital admission and ICU admission with proportion of patients with decreased left ventricular ejection fraction ≥10% and secondary endpoints cardiac structure and function.
- Multivariable mixed models will be used to estimate the association between serial measures of cardiac structure and function, need for mechanical ventilation, and in-hospital mortality.

Interventional Study

- Safety assessment of AT-001 based on reported adverse events
- Exploratory analyses with descriptive statistics to estimate effects of co-enrollment on safety outcomes
- Exploratory analyses with descriptive statistics to describe clinical outcomes in patients treated

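### Logistic and Cox regression are assigned to the registry's continuous cardiac endpoints, and Cox to an LVEF decline whose event time is not defined

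*Combined protocol and SAP*

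**What the plan says.** Section 4.2.1 makes the registry's primary endpoint binary: "Proportion of subjects with decreased left ventricular ejection fraction" of 10% or more from baseline. Section 4.2.2 lists nine secondary endpoints shared by the registry and the trial. Four are continuous changes, among them "Change in left ventricular ejection fraction", "Change in left ventricular end-diastolic diameter" and "Change in biomarkers of cardiac injury"; the fourth is end-systolic diameter. The other five are rhythm or conduction events, such as "Frequency of atrial fibrillation".

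The first registry item of section 10.4.2 reads "Multivariable logistic regression models and Cox Proportional Hazard models will be used to estimate the association between clinical variables at time of hospital admission"; variables taken on entry to the ICU are included as well. The outcomes it names are the LVEF decline "and secondary endpoints cardiac structure and function". The Protocol Summary repeats this. A second item names multivariable mixed models for the association between serial cardiac measures, need for mechanical ventilation and in-hospital mortality; the Summary's version leaves out ventilation. Section 10.4.3 is a single sentence: "The same analyses will be used for secondary endpoints".

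Section 10.1 states that no formal SAP exists, so no other document fills in the detail. Sections 7.1.1 and 7.3 describe extraction of clinically derived data from the medical record, and the Schedule of Events in section 20 contains no echocardiogram. The interventional trial is analysed descriptively and is not affected by this point.

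**The concern.** Logistic regression needs a binary outcome and Cox regression needs a dated event. A change in diameter or in a biomarker is neither. Following the text therefore means choosing a cut-point the plan does not give, possibly after seeing the data, and discarding information in the process.

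The second problem is Cox regression for the LVEF decline. Section 10.4.2 takes predictors at both hospital and ICU admission and does not say which starts the clock. It gives no event date, no censoring rule and no handling of death or discharge. LVEF is known only when a clinician orders an echocardiogram, so the decline lies somewhere between two irregular scans. A Cox model timed by the scan that reveals it is partly a model of how soon and how often patients are scanned. If sicker patients are imaged more often, admission predictors of imaging could be reported as predictors of decline. Those associations are what the registry hypothesis in section 10.2 is about.

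**Working it through.** There is no figure in the plan to reproduce. Section 10.5 calls the 500 registry patients a convenience sample and gives no alpha, effect size, numerical power or event rate. The check is therefore endpoint against model, followed by two illustrations on assumed inputs.

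**Endpoint against model (registry)**

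| Endpoint | Logistic | Cox | Mixed model as written |
|---|---|---|---|
| LVEF decline of 10% or more | Fits | Event time not defined | Not aimed at it |
| Change in LVEF | Only by cutting; the one available cut (10%) returns the primary endpoint | No event | Suitable type, different question |
| Change in end-diastolic and end-systolic diameter | No cut-point given | No event | Suitable type, different question |
| Change in biomarkers (through section 10.4.3) | No cut-point given | No event | Suitable type, different question |
| Five rhythm or conduction endpoints | Fits, if frequency means occurrence | Possible if onset is dated | Not aimed at them |

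The mixed models relate serial measures to ventilation and mortality, and the plan does not say which variable is the outcome. They are not assigned to the relation between admission variables and later cardiac change. No linear model or analysis of covariance is named.

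**Illustration 1: cost of dichotomizing.** For a normal outcome cut so that a proportion p are events, the relative efficiency is φ(z)²/[p(1−p)], where z is the upper-p normal quantile.

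- p = 0.10: z = 1.2816, φ(z) = 0.1755; 0.1755²/0.09 = 0.342; × 500 = 171.
- p = 0.15: 0.426; × 500 = 213.
- p = 0.20: z = 0.8416, φ(z) = 0.2800; 0.2800²/0.16 = 0.490; × 500 = 245.

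The 10-20% range is an assumption. It is borrowed from section 2.1, where it describes cardiac complications in general in severe disease.

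**Illustration 2: Cox regression on detection date.** Assumed: 500 patients, 300 replicates, a true decline in 30% by day 14, exponential stay with mean 10 days capped at 30, and 0.1 echocardiograms per day. A binary covariate has no effect on LVEF and changes only the imaging rate.

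- Equal imaging: median hazard ratio 1.02, rejection 4.7% (nominal 5%).
- Double imaging: 1.46, rejection 29%.
- Triple imaging: 1.71, rejection 56%.

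**Does logistic regression avoid this?** Under the same inputs, if patients without a scan count as non-events, the null covariate gives odds ratios of about 1.40 (double) and 1.69 (triple), with rejection of 20% or more and above 40%. If only imaged patients are analysed, the odds ratio is about 1.02 to 1.04. The analysis set therefore matters as much as the choice of model.

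**The case against.** The best defence is that most of the endpoints are served. Logistic regression suits the binary primary endpoint and the occurrence of the five rhythm or conduction events. LVEF has a stated cut-point of 10%. Mixed models, which suit serial continuous data, are named, and the sentence in section 10.4.3 can be read as covering them too. Daily extraction could record the date of the scan that shows the decline, and the eCRF, which is an attachment, is not available to check.

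All of this stands, and it limits the point. A reader might infer that the named models fail for the registry endpoints generally, or that no suitable model is named at all; the documents support neither. A reader might also infer that an event time cannot be observed. The supportable statement is that none is defined, and that without scheduled imaging only a detection date could be available.

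The defence does not remove the assignment in section 10.4.2. It ties logistic and Cox models expressly to the continuous structure and function endpoints, while the mixed models are directed at another association with no stated outcome.

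**Conclusion.** The concern holds in a limited form. Four continuous registry endpoints are given models that cannot analyse them as defined, and Cox regression is named for an LVEF decline without the rules that would make its time scale meaningful. Reading the text generously does not settle which model relates admission variables to cardiac change.

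The sizes are illustrative. The 34-49% assumes a normal outcome and a 10-20% event proportion that the plan does not state for any of these endpoints. It would be tempting to conclude that this registry of 500 will act like 171 to 245 patients; the documents do not support that, because nothing shows that all 500 will have paired measurements. The hazard ratios of 1.46 and 1.71 depend on the assumed imaging rates, stay and decline. They show the direction and possible scale of the bias, and do not predict it. The simulation also lets imaging depend on the covariate alone. If scans are ordered because a decline is suspected, restricting to imaged patients leaves some selection.

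**What to change.** Rewrite sections 10.4.2 and 10.4.3, and the matching Summary text, with one rule per endpoint type:

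- **Change in LVEF, diameters and biomarkers:** linear mixed models of the serial values on time and the admission predictors, with predictor-by-time terms to carry the association with change. Log-transform the biomarkers.
- **LVEF decline of 10% or more:** logistic regression among patients with a baseline and at least one follow-up LVEF. Do not count unimaged patients as non-events, and report how many are excluded. Drop Cox for this endpoint, or use an interval-censored model as a sensitivity analysis.
- **Cox regression:** only for events with a recorded date (arrhythmia, ventilation, death). State the time origin and censoring rule, and treat death or discharge as competing events where they apply, since section 5.5 ends registry follow-up at discharge or 30 days.

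The cost is a change of wording and slightly more analysis work; no new procedure is needed. The LVEF analysis will be limited to patients imaged in routine care. How many will have a baseline value cannot be told from the documents.

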10.4.4 Safety Analyses

Adverse events will be analyzed as summary statistics and coded by MedDRA.

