2.4 Potential Risks & Benefits

2.4.1 Known Potential Risks

In subjects enrolled in the prospective registry, the only risk is potential breach of confidentiality.

In subjects enrolled in the interventional trial, additional risk is associated with investigational agent. In the completed first in human study (Study AT-001.1001) AT-001 was generally well tolerated with no safety issues identified. There were no SAEs considered treatment-related and no AEs causing discontinuation of study treatment. No clinically relevant changes in vital signs, ECG or clinical safety laboratory values were noted.

Potential risks of AT-001 based on non-clinical data and previous experience with other aldose reductase inhibitors include:

- Acute hypersensitivity reactions
- Hepatic toxicity, including fatal hepatic necrosis
- Renal toxicity: Nephrolithiasis (calculi and pelvic dilation suggestive of an obstructive mechanism leading to development of pyelonephritis were reported in female rats in a 6-month chronic toxicology study. These renal findings were not reproduced in dogs in a 9-month chronic toxicology study)
- Gastrointestinal events, including nausea, vomiting, diarrhea, flatulence, abdominal pain
- Ocular effects (two cases of non-adverse, reversible multifocal pinpoint corneal opacities in a 28day toxicology study in dogs, which was not reproduced in a 9- month chronic toxicology study)
- Hypotension and dizziness
- Skin rash/eczema
- Decreases in hemoglobin, erythrocyte count, and lymphocyte count
- Reduction in total protein in blood

The incidence of these side effects for short-term exposure to AT-001 in COVID-19 patients is unknown. We anticipate that patients with COVID-19 infection will receive concomitant treatments including off-label use of FDA-approved drugs, anti-viral therapy with remdesivir under expanded access or emergency use access, and treatment with hydroxychloroquine, convalescent sera, and/or IL-6 inhibitors within the context of clinical trials. Based on knowledge of the pathophysiology of COVID-19 infection and the pharmacology of AT-001, we do not anticipate that these concomitant medications will increase risk associated with AT-001. Patients with COVID-19 infection are known to be a high risk of complications including

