7.2 Laboratory Procedures/Evaluations

7.2.1 Clinical Laboratory Evaluations

Standard of care laboratory procedures will be performed; results will be recorded in the research database There are no study-related laboratory evaluations.

- **Hematology:** hemoglobin, hematocrit, white blood cells (WBC) with differential count, platelet count.
- **Biochemistry:** serum electrolytes, blood urine nitrogen, creatinine, total bilirubin, alanine aminotransferase (ALT), aspartate aminotransferase (AST), albumin, total protein, calcium, magnesium, phosphate, troponin-I, brain natriuretic peptide, ferritin, CRP, ESR, IL-6, .
- **Urinalysis:** dipstick urinalysis, including protein, hemoglobin and glucose; if dipstick is abnormal, complete urinalysis with microscopic evaluation is required.
- **Pregnancy test**, usually to be done within 24 hours prior to study intervention and results must be available prior to administration of study product.

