8.1.1 Definition of Adverse Events (AE)

An *adverse event* (AE) is any symptom, sign, illness or experience that develops or worsens in severity during the course of the study. Intercurrent illnesses or injuries should be regarded as adverse events. Abnormal results of diagnostic procedures are considered to be adverse events if the abnormality:

- results in study withdrawal
- is associated with a serious adverse event
- is associated with clinical signs or symptoms
- leads to additional treatment or to further diagnostic tests
- is considered by the investigator to be of clinical significance

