10.1 Statistical and Analytical Plans (SAP)

Due to the urgent COVID-19 crisis, there is no formal SAP.

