10.2 Statistical Hypotheses

The null hypothesis for the registry study is that there are no significant associations between clinical characteristics at study entry and subsequent occurrence of cardiac dysfunction, lung dysfunction or death in hospitalized patients with COVID-19 infection.

There will be no hypothesis testing for the interventional trial. The primary endpoint is safety of AT-001 based on descriptive statistics and qualitative evaluation of adverse event monitoring. Descriptive statistics will be used to assess frequency of secondary endpoints without hypothesis testing.

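### Recorded laboratory values for AT-001's named hepatic, hematologic and total-protein risks have no planned summary, so a modest consistent shift can go unreported in the primary safety result

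*Combined protocol and SAP*

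**What the plan says.** **Endpoint and analysis (Combined protocol and SAP).** Section 4.2.1: "Primary Endpoint for Embedded Clinical Trial: Safety of AT-001 based on adverse events reporting". Section 10.2 rules out hypothesis testing for the interventional trial and adds: "The primary endpoint is safety of AT-001 based on descriptive statistics and qualitative evaluation of adverse event monitoring". Section 10.4.2 lists "Safety assessment of AT-001 based on reported adverse events", and section 10.4.4 states in full: "Adverse events will be analyzed as summary statistics and coded by MedDRA". No further plan exists, because section 10.1 says: "Due to the urgent COVID-19 crisis, there is no formal SAP".

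**Named risks.** Section 2.4.1 lists hepatic toxicity, reduced total protein, and "Decreases in hemoglobin, erythrocyte count, and lymphocyte count". It also lists a renal risk.

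**Data held.** Section 7.2.1: "Standard of care laboratory procedures will be performed; results will be recorded in the research database". Its list includes ALT, AST, total bilirubin, creatinine, hemoglobin, white cells with differential, and total protein. It omits the erythrocyte count. It adds that no laboratory test is done for the study itself.

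**From value to event.** Section 8.1.1 makes an abnormal result an adverse event on any one of five grounds: study withdrawal, association with a serious event, association with signs or symptoms, further treatment or tests, or that it "is considered by the investigator to be of clinical significance".

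**Other laboratory outcomes.** The only laboratory change that is an endpoint is in cardiac injury biomarkers (section 4.2.2).

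**The concern.** The protocol names risks that show first as laboratory changes and stores the measurements, yet its primary safety result uses only those that someone has classed as events. A mild fall in lymphocytes or total protein, or a mild ALT rise, in a patient who needs no treatment or extra test for it may meet none of the five grounds. In a COVID-19 inpatient it is also easily put down to the disease. If the same mild change occurred in most of the 20 patients, the report could show few hepatic or hematologic events while the trial's own database held a consistent within-patient shift.

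The trial is open-label, so the event count also depends on unblinded judgement and on how closely each patient is tested. A summary of the recorded values would remove the dependence on labelling. It would still depend on which samples were taken.

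**Working it through.** The plan gives no figure to reproduce: section 10.5 calls the 20 interventional participants a convenience sample. The check is first textual, then an illustration of scale.

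**1. Risks against data against analysis**

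| Risk (2.4.1) | Recorded value (7.2.1) | Planned summary (10.4) |
|---|---|---|
| Hepatic toxicity | ALT, AST, total bilirubin | Only if reported as an adverse event |
| Lower hemoglobin | Hemoglobin, hematocrit | Same |
| Lower erythrocyte count | Not listed | Same |
| Lower lymphocyte count | White cells with differential | Same |
| Lower total protein | Total protein, albumin | Same |
| Renal toxicity | Creatinine, urea nitrogen | Same |

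Section 10.4.1 mentions data distributions, and section 10.4.2 mentions clinical outcomes in treated patients. Neither names a laboratory variable or a change from baseline. Section 10.4.6 covers baseline only.

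**2. Scale, one on-treatment value per patient**

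Assumptions, none from the documents: 20 patients with paired values; normally distributed change in units of its own SD; true mean shift d = 0.75; abnormal beyond 2 SD; a fraction q of abnormal patients labelled as having an adverse event.

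- Share abnormal = 1 − Φ(2 − 0.75) = 0.1056.
- Expected labelled = 20 × 0.1056 × q. Chance of none = (1 − 0.1056q)^20.

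| q | Expected labelled | Chance of none |
|---|---|---|
| 1 | 2.11 | 0.107 |
| 0.5 | 1.06 | 0.338 |
| 0.25 | 0.53 | 0.585 |

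The threshold matters as much as q. With q = 1, the chance of none is 0.006 at 1.5 SD, 0.107 at 2 SD and 0.782 at 3 SD.

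**3. Five on-treatment values per patient**

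Data are collected daily for up to 14 days (section 7.3), so one value is too few. Assume five values, each compared with the same pre-dose value. The correlation between on-treatment values is taken as 0 to 0.8; sharing the pre-dose value makes the correlation between changes 0.5 to 0.9. By simulation, the share of patients with at least one change beyond 2 SD at d = 0.75 is 0.306 to 0.183. With q = 0.5:

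- Expected labelled: 20 × 0.306 × 0.5 = 3.06, down to 20 × 0.183 × 0.5 = 1.83.
- Chance of none: (1 − 0.153)^20 = 0.036, up to (1 − 0.0915)^20 = 0.147.

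Repeated sampling therefore makes complete silence much less likely. About two or three labelled patients in 20 would still not show that the whole group had moved.

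**4. What a summary of values gives**

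With 20 pairs, the 95% CI half-width for a mean change is t(0.975, 19)/√20 = 2.093/4.472 = 0.468 SD. It widens with fewer pairs.

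**5. Which change to summarise**

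Under the model in step 3 with no true shift (d = 0), a 95% CI for mean change to the worst of five values excludes zero in about 36% to 99% of simulated trials. For change to the last value the figure is 5%. The worst of several values is adverse on average by construction, so it suits a shift table but not a mean with a CI.

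**The case against.** The strongest reply is that the protocol does more than wait for an unguided opinion.

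- Investigator judgement is one of five grounds in section 8.1.1, and the ground of further treatment or tests is broad for inpatients.
- Section 2.4.1 makes membership of the named-risk list a reason to suspect the drug. Section 8.7 does the same with biological plausibility, and section 8.2.2 holds the study product always suspect.
- Section 8.7 requires daily laboratory review, a full review of each patient's course after 7 and 14 days of treatment, and a summary of those reviews to the IRB.
- The study is small, descriptive and uncontrolled. The values are kept, and nothing bars tabulating them later.

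All of this stands, and it rules out several stronger readings that a reader might infer:

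- *That a shift must go unreported, or counts only when an investigator says so.* The routes above may catch it.
- *That the protocol declares mild laboratory changes expected.* Sections 2.4.1 and 8.7 anticipate organ dysfunction and septic shock, with associated laboratory abnormalities. They do not say this of a mild change in a patient without organ failure.
- *That a CI for mean change excluding zero would show drug harm.* COVID-19 itself moves these values, so zero is not the no-drug value, and section 10.2 plans no testing.

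The reply does not close the gap. Each safeguard works case by case, and none commits to a summary of measured values across patients. A table chosen after the data are seen is weaker than one named beforehand.

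Separately, section 8.3 requires all adverse events to be documented regardless of relationship, while section 8.7 says only suspected treatment-related ones will be reported. The two must be reconciled.

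**Conclusion.** The concern holds in a limited form. Sections 4.2.1, 10.2, 10.4.2 and 10.4.4 confine the planned safety result to adverse events. The values matching most of the named risks are already recorded, and no section summarises them across patients. A modest consistent shift can therefore be absent from the primary safety result.

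This conclusion rests on the text. The arithmetic only gives scale. With half of abnormal patients labelled, the chance of no labelled patient runs from about 4% to 34%, depending on the number and correlation of values per patient; other thresholds and labelling rates widen that range. The 20 complete pairs are optimistic, because sampling is standard of care. The eCRF and Investigator Brochure are separate attachments and were not available.

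The change is worth making before analysis because it serves the trial's own primary question at little cost. It does not invalidate the adverse event analysis.

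**What to change.** Add to section 10.4.4, for the interventional safety set:

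> *For ALT, AST, total bilirubin, creatinine, hemoglobin, lymphocyte count and total protein, change from the last pre-dose value to the last on-treatment value will be summarised by median, IQR, mean with 95% CI, and number of patients with paired values. A shift table will show the pre-dose against the worst on-treatment reference-range category. No CI will be given for change to the worst value. Every recorded value is used, whether or not it was called an adverse event.*

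Extend the safety line in section 10.4.2 so that it rests on recorded laboratory values as well as reported adverse events.

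State two limits beside the tables. First, the changes combine drug and disease course, because the analysis has no control group. (The Protocol Summary calls the trial randomized against standard of care; sections 4.1, 10.2 and 10.3 describe no comparison arm, and this should be reconciled.) Second, the worst-value category is adverse on average even without a drug effect.

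The cost is a few lines of protocol and a few tables from data already held, with no new samples or visits. The downside is small: some pairs will be missing, and the tables need the two caveats.
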